#### *Resource utilisation*

We will use a self-reported health and social services resource utilisation survey with a 3-month recall period (collected at the 12-week follow-up point only). This will include tracking appointments with GPs, consultants, OTs, PTs, if there is a change in their medications, or if they access any complementary therapies etc during period of study.

#### Adverse Events

This population is particularly at risk of falls. Participants will be warned of this risk and asked to ensure they undertake all exercise and other activities with due care and caution. All participants will be asked to record any falls for the duration of the study. We will also record adverse events such as admissions to hospital and for what reason.

#### Data management

Data management will follow the Data Protection Act 2018 (DPA 2018) and UK General Data Protection Regulation (UK GDPR), and the University of East Anglia's Research Data

Management Policy. The legal basis for processing the data as listed in Article 6(1) of the UK GDPR; because this allows us to process personal data when it is necessary to perform our public tasks as a University.

- The data controller is the University of East Anglia.
- The University's Data Protection Officer can be contacted at [contact]
- More about participant's data protection rights is available at the Information Commissioner's Office (ICO).
- If participants are unhappy with how their personal data has been used, they will be asked to contact the University's Data Protection Officer at [contact] in the first instance.

## Data security

Only members of the research group (members are listed at the start of this protocol) will have access to the data during the project.

Most of the assessments and consent will be recorded online using the Qualtric survey platform. However, to ensure accessibility for participants with disability access needs, participants will be offered hard copy survey and consent forms to be posted to them (including a postage paid return envelope). If participants take up this option, the information on these hard copies will be transcribed by SA into the Qualtrics surveys. All hard copy surveys and consent forms will be destroyed as soon as the data is transcribed to the Qualtrics platform.

The data will be downloaded from the Qualtrics platform to the secure UEA server, and the original data will be deleted from the Qualtrics platform by September 31st, 2025. The contact details will be kept only until everyone involved in the trial has been sent a link to the online fatigue management intervention i.e., 14 weeks after randomisation (September 31st, 2024, latest). After this we will destroy the contact details and keep the anonymised dataset of results.

Project data will be deleted from the UEA shared drive 10 years after the end of the project (i.e., 31st September 2035). Only anonymised data will be shared externally (e.g., in reports and publications).

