#### Randomisation and stratification

Upon completion of baseline data, participants will undergo randomisation to either the intervention arm (fatigue management) or the control arm (waitlist) utilizing the Sealed Envelope website. Sealed Envelope offers a robust online software application for randomising patients into clinical trials and capturing case report form data (EDC and ePRO).

The Simple randomisation service provided by Sealed Envelope will be employed for this trial. This uses a pseudo-randomisation number generator, and will allocate participants in a 1:1 ratio to ReFresh or wait list. To ensure a reasonably even distribution of patients in the 2 arms throughout the course of the trial, patients will be allocated in randomly permuted blocks of 4 and 6 (Sealed Envelope Ltd. 2022).

For the trial, a unique password will be assigned. Authorized personnel with the password will have the capability to conduct new randomisations. The results will be promptly displayed on-screen and emailed to both the trial administrator and the assigned individual overseeing the randomisation process, ensuring transparency and accountability.

Upon allocation participants will be sent an email informing them of their allocation. If allocated to the ReFresh group they will be sent the link to the ReFresh online program https://www.uea.ac.uk/web/groups-and-centres/projects/fatigue-management-in-parkinson-s/refresh-study-getting-started. If they are allocated to the waitlist group they will be told they will be contacted again in 12 weeks to complete the end point survey, and then at 16 weeks with the link to the ReFresh program (to ensure no contamination of the control group).

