## Blinding

Blinding to group allocation will not be possible as participants will know whether they had access to the online fatigue management program. All assessments will be completed by participants via online surveys. The trial data will be analysed by SA who will not be blinded to allocation.

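### Paper surveys and consent forms are destroyed as soon as one person has keyed them, so in-range entry errors on paper forms cannot be checked against source and the participant's own consent record is lost

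*Protocol*

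**What the plan says.** Protocol, Data security: online entry is the main route ("Most of the assessments and consent will be recorded online using the Qualtric survey platform"), but participants with disability access needs are offered posted paper surveys and consent forms. For these, "the information on these hard copies will be transcribed" into the survey platform by one team member, identified by initials. The section continues: "All hard copy surveys and consent forms will be destroyed as soon as the data is transcribed to the Qualtrics platform". It describes no scan, second entry or comparison with the paper before destruction. Contact details are destroyed once every participant has been sent the programme link. The anonymised dataset is kept, and project data are deleted 10 years after the project ends.

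Protocol, Blinding: the same team member analyses the data and is someone "who will not be blinded to allocation". The section also states "All assessments will be completed by participants via online surveys", which does not fit the paper option.

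Protocol, Randomisation and stratification: "Upon completion of baseline data, participants will undergo randomisation".

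**The concern.** For a participant who answers online, the platform holds that person's own entry. For a participant who answers on paper, the platform holds only a copy made by the research team, and the paper is the sole source. If the paper is destroyed on transcription, a misread or mis-keyed answer that is a permitted value stays in the data for good. The loss is irreversible, and it falls on the group for whom the paper route was created.

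Two further things are at stake. First, the consent form. The inclusion criteria infer competence to consent from completing the online surveys, which paper users do not do, so the form they filled in is their main evidence of consent. What remains is an entry made by someone else. Second, the person who keys the 12-week paper forms knows the allocation and later runs the comparison, so no one independent of the analysis stands between the paper and the result.

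**Working it through.** The protocol gives no figure to reproduce here beyond the sample size, 2 × 20 = 40. The point is procedural and is checked first by setting the sections side by side, then scaled by arithmetic.

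**Which data are exposed**
- Online scores: no transcription step, so no exposure.
- Paper baseline and consent forms: exposed to plain keying error. Randomisation follows completion of baseline data, so no allocation exists when these forms are filled in. Assuming they are keyed before the participant is randomised, allocation cannot influence the keying.
- Paper 12-week forms: exposed to plain keying error and, because the transcriber is the unblinded analyst, to allocation-related error.

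**What could still be caught**
- Out-of-range values can be seen without the paper.
- A doubtful entry can be queried with the participant while contact details are held. Data security puts the sending of the last link at 14 weeks after randomisation, which leaves about 14 − 12 = 2 weeks after the 12-week survey for the last person randomised, and longer for those randomised earlier.
- An in-range error that nobody suspects cannot be found by either route.

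**Size of one error (MFIS: 21 items, total 0 to 84; 20 per arm)**
- Maximum per item: 84/21 = 4 points.
- Shift in an arm's mean change = (forms affected × points of error per form)/20.
- One form, one item wrong by the full range: 1 × 4/20 = 0.2 points.
- Four forms, 8 points each in one direction: 4 × 8/20 = 1.6 points.
- Six forms, 12 points each in one direction: 6 × 12/20 = 3.6 points.

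The numbers of forms and the error sizes are assumptions. The difference between arms moves by the same amount if only one arm is affected.

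**Chance of at least one wrong item at 12 weeks**

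The two fatigue scales have 21 + 16 = 37 items. With independent errors at rate e per item and f paper forms, the chance is 1 − (1 − e)^(37f). Both e and f are assumed.

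| e | f = 2 | f = 4 | f = 8 |
|---|---|---|---|
| 0.1% | 7% | 14% | 26% |
| 0.5% | 31% | 52% | 77% |
| 1% | 53% | 77% | 95% |

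So an error somewhere may be likely, but each one is worth at most 0.2 points on an MFIS arm mean.

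**Effect on the variance**

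The first aim is the size and variance of the difference in change. One independent error of d points in one change score adds on average d²/20 to that arm's variance, and d²/40 to the pooled variance.
- d = 4: 16/40 = 0.4, which is 0.4% of the variance if the SD is 10 (0.4/100) and 0.2% if it is 15 (0.4/225).
- d = 20: 400/40 = 10, which is 10% if the SD is 10 and 4% if it is 15. This needs at least 20/4 = 5 items wrong by the full range in one direction on one form.

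The SDs are assumed; the protocol gives none.

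**The case against.** Most data are typed in by participants, the number of paper users may be zero, and the arithmetic above shows that isolated errors hardly matter in a pilot that disclaims an accurate assessment of efficacy. All of that stands, and it limits the weight of the point.

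It can also be said that checking procedures belong in a data-management plan, and that the Data management section defers to a university policy not shown here. That would answer a complaint about missing detail. It does not answer this one, because the protocol states the destruction rule, and a rule that removes the paper on transcription leaves nothing for a later check to use.

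Several stronger readings are tempting, and the documents do not support them:
- A reader might infer that errors or bias in the fatigue scores in general cannot be detected. This applies only to in-range errors on paper forms.
- A reader might infer that every paper form is keyed with knowledge of the arm. The order of baseline and randomisation confines this to the 12-week forms.
- A reader might picture one slip of 40 points moving an arm mean by 40/20 = 2 points. Forms are transcribed into the surveys, nothing says that totals are keyed, and 40 points would need at least 40/4 = 10 items wrong by the full range in the same direction.
- A reader might infer that all proof of consent disappears. A transcribed entry remains at first, though it is not the participant's own record.
- A reader might treat the unblinded analyst as a defect in itself. The status is openly declared, and the Efficacy Analyses section already fixes the test and last observation carried forward for incomplete data. The choice between the two fatigue scales is less constrained, but masking would not supply the missing selection rule.

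**Conclusion.** The point holds in a limited form. As written, the protocol makes in-range keying errors on paper forms unverifiable at both time points and discards the paper user's own consent record. Allocation-related error is possible only at 12 weeks. The expected numerical effect is small: at most 0.2 points on an MFIS arm mean per wrong item, reaching the 1.6 to 3.6 points above only if several items on several forms err in one direction. This rests on 20 participants per arm, item-level keying, baseline forms keyed before randomisation, and an unknown number of paper users. The case for changing the text is that destruction cannot be undone and retention costs very little. It is a cheap improvement, not a threat to the trial's conclusions. The mismatch between the Blinding and Data security sections on how assessments are completed is a plain inconsistency and should be corrected in any event.

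**What to change.** 1. In Data security, replace immediate destruction with retention: keep the paper forms, or scans on the secure university server, until an existing team member other than the transcriber has checked the entries and the database is locked.
2. Keep paper consent forms securely, apart from the anonymised dataset, for a stated period. Reconcile that period with the plan to destroy contact details, since a signed form identifies the participant.
3. In Blinding, replace the statement that all assessments are completed online with one that acknowledges the paper route and who keys it.
4. Optional: run data cleaning and the primary fatigue comparison on a file with arms coded A/B, without module data or the Canadian Occupational Performance Measure (COPM), which only the ReFresh group completes. Where possible, have the 12-week paper forms keyed by someone other than the analyst. Masking would be only partial, because anyone who has keyed a form containing the COPM has seen the arm.

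Cost: a few hours of existing staff time, short-term storage, and wording changes to the protocol and information sheet, with any data-protection or ethics review these need. The sample size and the visit schedule do not change.

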## Statistical analyses

#### **Baseline Comparisons**

The SPSS statistical program will be used to analyse the data. Baseline comparability of the groups by demographics will be described using descriptive statistics. Where data appears to be non-normally distributed according to the Shapiro-Wilks test, medians and interquartile ranges will be used to describe the data. Where data is normally distributed, means and standard deviations will be used.

#### **Efficacy Analyses**

As this is a pilot RCT an accurate assessment of the efficacy of the intervention cannot be determined as the study is insufficiently powered. However, we will analyse the primary outcome measure at 12 weeks using the parametric student-t test for comparing mean change between the two intervention groups.

Intention to Treat (ITT) analyses will be performed for all outcomes and will comprise of all patients who had been randomised. For the intervention group, this was irrespective of their compliance with the ReFresh program. The principle of ITT was adopted as it provides a pragmatic estimate of the benefit of a change in treatment policy compared to the potential benefit in patients who receive treatment exactly as planned. As the ReFresh program was planned for delivery over a six-week period, some participants may not have received all the planned sessions. As this is more likely to reflect usual practice, primary analyses of all outcomes were conducted according to the ITT principle. Per Protocol (PP) analyses was planned for participants who had not deviated from the ReFresh protocol in such a manner that the assessment of efficacy could be biased. This was defined as patients accessing at least four out of six ReFresh modules. Imputation of missing/incomplete data is planned to use last observation carried forward method for all outcome measures.

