#### Method

#### Design

A pilot randomised controlled trial with **two parallel comparator groups**; the ReFresh online fatigue management program versus a wait list group who will receive treatment as usual, and then access the ReFresh online course at week 14 to ensure all end point data is gathered. We will recommend participants access one **module per week** i.e. six modules over six weeks, and undertake at **least three 30 minute sessions of exercise per week**. The primary outcome will be fatigue at 12 weeks. All measures will be unblinded as it is impossible to blind participants as to whether they have accessed the web site or not.

This pilot study will check study processes (e.g., recruitment, randomisation, treatment, follow-up assessments) all run smoothly, and determine the acceptability and practicality of the ReFresh intervention. It will also appraise the feasibility and sensitivity of two fatigue measures in order to decide which measure will be the primary outcome measure in the fully powered RCT this pilot study will inform. The fatigue measures are the Parkinson's Fatigue Scale (PFS) (Baghoori 2017) and the Modified Fatigue Impact Scale (MFIS) (Fisk et al., 1994). These will be measured at baseline and 12 weeks. Once the primary measure is selected it will inform the number of participants required for a fully powered RCT.

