## Sample size

The sample size of feasibility and pilot studies is generally influenced by the need to confidently estimate outcome parameters, such as standard deviation, for use in the sample size calculation of a definitive trial. According to Lancaster, Dodd, and Williamson (2004), a sample size of 30 is often considered a good rule of thumb.

We will adhere to this guideline by recruiting 20 participants for each arm of the study, resulting in a total of 40 participants. This sample size will allow us to collect sufficient data to estimate outcome parameters effectively and inform the design of future definitive trials.

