#### Outcomes

Assessments will take place at baseline and 12 weeks after randomisation.

We anticipate that the ReFresh program will improve fatigue. In this pilot RCT we will use two measures of fatigue; the Parkinson's Fatigue Scale (PFS) (Baghoori 2017) and the Modified Fatigue Impact Scale (MFIS) (Fisk et al., 1994). These two measures assess related but not identical concepts. The PFS focusses on the experience of fatigue with some items that examine its impact on activities. Whereas the MFIS focusses far more on the impact having fatigue has on physical, social, and cognitive activities. We are unsure whether the ReFresh program will just impact on the sense of fatigue, or whether it will impact on participant's activity levels, so we will use both measures to determine which is most sensitive to any changes caused by the ReFresh program. MFIS is commonly used in fatigue research, and so these results could be more easily compared against other fatigue management protocols. The MFIS has excellent psychometric properties in multiple sclerosis populations; with internal consistency, Cronbach  $\alpha$  of 0.92 (Kos 2005), and a testretest reliability intraclass correlation coefficient (ICC) of 0.91, (Kos 2003). Although MFIS was not developed for Parkinson's it has been validated with this patient population; where it has high internal consistency, Chronbachs  $\alpha$ =0.96 (Schiehser 2012). However, the PFS was specifically developed and validated in people with Parkinson's (Baghoori 2017) and may therefore be more sensitive to disease specific factors. It is also a robust measure with a high internal consistency (Chronbach's  $\alpha$ =0.98) and good test-retest reliability Spearman R mean 0.63±0.06). The data from this pilot will allow us to refine the design of the planned

fully powered RCT to ensure its primary outcome uses the measure most likely to be sensitive to the changes possible from the ReFresh program.

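### The primary fatigue comparison is an unadjusted t test on change; adjusting for the pre-randomisation baseline score would be more precise and would not over-correct chance imbalance

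*Protocol*

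**What the plan says.** The Efficacy Analyses section names the test: the primary outcome at 12 weeks is analysed "using the parametric student-t test for comparing mean change between the two intervention groups". No baseline covariate appears there or elsewhere in the protocol.

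The covariate will be available. Of the two fatigue scales, the Design section says "These will be measured at baseline and 12 weeks", and the Randomisation and stratification section says "Upon completion of baseline data, participants will undergo randomisation".

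That section also says that the system "will allocate participants in a 1:1 ratio to ReFresh or wait list" and that "patients will be allocated in randomly permuted blocks of 4 and 6". Blocks of this kind balance numbers only. Despite the section's title, no stratification factor is named.

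The Sample size section plans "recruiting 20 participants for each arm of the study, resulting in a total of 40 participants". The Aims section puts first the estimation of the size and variance of the between-group difference in change, to be used for sizing a full trial.

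**The concern.** A change score subtracts the whole baseline value. With equal SDs at the two times, the best linear prediction of the 12-week score uses only r times the baseline value, so full subtraction goes too far whenever r is below 1. This has two effects. The estimated difference carries more variance than the data require. And if one arm starts more fatigued by chance, the change-score estimate is pushed in the opposite direction.

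The pilot makes no confirmatory claim, so the matter at stake is its first aim. The estimate and the variance carried to the definitive trial are that aim's product. They should be as precise as the data allow and should match the model that the definitive trial will use.

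**Working it through.** **The plan's own figure.** 20 × 2 = 40, which agrees with the stated total. The number rests on a rule of thumb ("a sample size of 30 is often considered a good rule of thumb"). No alpha, power, effect or SD is stated, so there is no power calculation to reproduce.

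**Inputs.**
- n = 20 per arm (Sample size).
- r for the PFS: the Outcomes section gives test-retest reliability as "Spearman R mean 0.63±0.06". Used as a proxy: 0.63, range 0.57 to 0.69.
- r for the MFIS: the same section gives a test-retest ICC of 0.91 in multiple sclerosis. Used as a proxy.
- r = 0.5: an assumption, in case the 12-week correlation is lower than the retest figures.
- Equal SD at baseline and 12 weeks, set to 1: an assumption.

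**Precision.** Per participant, Var(change) = 2(1−r) and Var(ANCOVA) = 1−r². The large-sample ratio is (1−r²) / [2(1−r)] = (1+r)/2. Estimating the slope costs a factor 1 + 1/(N−4) = 37/36 at N = 40. The 95% CI half-widths below are in SD units, with 38 df for change and 37 df for ANCOVA.

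| r | 2(1−r) | 1−r² | (1+r)/2 | × 37/36 | Variance cut | Half-width, change | Half-width, ANCOVA |
|---|---|---|---|---|---|---|---|
| 0.50 | 1.00 | 0.750 | 0.750 | 0.771 | 23% | 0.640 | 0.563 |
| 0.63 | 0.74 | 0.603 | 0.815 | 0.838 | 16% | 0.551 | 0.504 |
| 0.91 | 0.18 | 0.172 | 0.955 | 0.982 | 2% | 0.272 | 0.269 |

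Over the PFS range 0.57 to 0.69 the ratio in the fifth column runs from 0.81 to 0.87. A simulation of 40,000 trials with 20 per arm gave 0.767, 0.833 and 0.979 for the three rows.

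**Break-even.** (1+r)/2 × 37/36 = 1 gives r = 72/37 − 1 = 0.946. Below that, ANCOVA is more precise at this size.

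**Chance imbalance.** The SD of the baseline mean difference is √(2/20) = 0.316. P(|difference| > 0.3 SD) = P(|Z| > 0.3/0.316) = 0.34. Given a baseline difference d, the change-score estimate shifts by −(1−r)d. For d = 0.3 that is 0.15 SD at r=0.5, 0.37 × 0.3 = 0.11 SD at r=0.63, and 0.03 SD at r=0.91, each in the opposite direction. At r=0.63 the simulated correlation between the estimate and the baseline difference was −0.44 for change and 0.00 for ANCOVA.

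**Share of variance.** The part of the change-score estimate's variance that comes from baseline imbalance is (1−r)²(2/n) / [2(1−r)(2/n)] = (1−r)/2, which is 18.5% at r=0.63 and 4.5% at r=0.91.

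**Definitive trial.** If it is analysed by ANCOVA but sized on the change-score SD, the inflation at r=0.63 is 1/0.815 = 1.23. As an illustration with an assumed effect of 0.5 SD, 80% power and two-sided 5%, this is 47 against 38 per arm.

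**The case against.** The strongest reply is that nothing here is wrong. Under 1:1 randomisation the t test on change is unbiased with a valid type I error. It matches an aim that is itself worded as a difference in change, and the protocol says that the pilot lacks the power to judge efficacy. All of that stands. It does not favour the t test, however: a model of change with baseline as covariate gives the same arm coefficient as a model of the 12-week score, so the aim is served either way.

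The reply also limits the size, in ways that stand:
- Test-retest reliability is only a proxy for r. The retest interval is not given, and a mean with a spread may be an average of several coefficients.
- For the MFIS the gain is negligible if r is near 0.91.
- The pilot's t test does not by itself oversize the later trial. Both SDs and r can be recovered from the data, and if the later trial also analyses change, the change-score SD is the right input.
- Sampling error is larger than the gain: with 38 df, the 95% range of true to estimated variance is about 0.67 to 1.66.

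A reader might infer more than the documents support:
- That regression to the mean dominates the result. It does not: at r=0.63 baseline imbalance accounts for 18.5% of the estimate's variance.
- That a material imbalance is likely. A difference above 0.3 SD has a 34% chance, and the resulting 0.11 SD shift is about a fifth of the 0.551 SD half-width.
- That r=0.63 is where change scores lose most. The loss keeps growing as r falls.

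**Conclusion.** The point holds as one of efficiency and of conditional over-correction, not of validity. At 20 per arm, with equal SDs, ANCOVA is more precise for any r below about 0.946, which covers both reliability figures quoted in the protocol. The gain in variance is about 23% at r=0.5, 16% at r=0.63 and 2% at r=0.91.

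The direction is secure; the size is not, because the documents do not give the 12-week correlation. The 23% oversizing of the definitive trial is conditional on three things: that trial uses ANCOVA, it is sized on the change-score SD, and r is 0.63. It should not be quoted without those conditions.

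**What to change.** In Efficacy Analyses, replace the t test with a linear model of the 12-week score on arm and the same scale's baseline score, fitted separately for MFIS and PFS. Report the adjusted difference with its 95% CI. Report also the residual SD and the baseline to 12-week correlation for each scale, so that the definitive trial can be sized for the same model.

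The cost is a sentence or two of wording and one degree of freedom (37 instead of 38). No extra data are needed, and SPSS, the package the protocol names, fits the model directly.

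The change does not deal with the planned last observation carried forward. With only two assessments, that rule sets the change of anyone without 12-week data to zero and distorts both the variance and the correlation. It is a separate matter.

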#### Intervention group

Participants randomised into this arm will gain access to the online fatigue management web page https://www.uea.ac.uk/web/groups-and-centres/projects/fatigue-management-in-parkinson-s/refresh-study-getting-started. Participants will progress through the online resources at their own pace but are recommended to complete one module per week of information, and to participate in an exercise program at least three times per week. There are six modules (see Appendix 1 for more detail)

Participants will be tracked in their use of the online resources and defined as completing the fatigue management if they accessed at least four of the six modules.

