## Control group

Participants in the control arm were waitlisted for 4 months to access the online fatigue management program. They received usual care for their Parkinson's, i.e., patients will attend consultant and nurse specialist appointments as scheduled based on their clinical needs. No additional contact or information regarding fatigue management will be provided.

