#### Adherence

We will track the completion of each module of the online ReFresh program by tracking access online web page hits, documents downloaded or requested in hard copy, exercise / activity / fatigue diaries.

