## For Participants in Waitlist Group:

Subject: Allocation Decision: You are in the Waitlist Group

Dear ......

Congratulations! We are pleased to inform you that you have been allocated to the T the waitlist group. Thank you for your participation and commitment. Being a part of the waitlist group allows us to compare your results against the group that get immediate access to the ReFresh program. In a disease as variable as Parkinson's this is critical to allow us to determine if any differences are "real" and useful,

We will be in touch with you in 12 weeks to provide you with the endpoint survey link and further instructions. Completing the surveys requested is critically important to allow us to properly assess the ReFresh program.

We will then be in touch with you in 16 weeks where we will provide your with the link to the ReFresh online program. Your participation at this point will not be recorded.

If you have any questions or concerns, please feel free to reach out to us.

Best regards,

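### The per-protocol set is defined only by module access, which waitlist participants cannot have before the endpoint: it holds either no controls or selected adherers against all controls

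*Protocol*

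**What the plan says.** The Protocol's Efficacy Analyses section makes intention-to-treat, on everyone randomised, the primary analysis. It compares mean change at 12 weeks between arms with a t test. It then introduces a second set: "Per Protocol (PP) analyses was planned for participants who had not deviated from the ReFresh protocol in such a manner that the assessment of efficacy". That sentence closes by naming bias as the consequence to be excluded. The next sentence gives the whole operational definition: "This was defined as patients accessing at least four out of six ReFresh modules".

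The same threshold appears once more, under Intervention group, where participants are "defined as completing the fatigue management if they accessed at least four of the six modules".

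For the waitlist arm, the Control group section says "No additional contact or information regarding fatigue management will be provided". Randomisation and stratification has these participants contacted at 12 weeks for the endpoint survey, "and then at 16 weeks with the link to the ReFresh program (to ensure no contamination of the control group"). The Design section puts access earlier: "and then access the ReFresh online course at week 14 to ensure all end point data is gathered". The waitlist allocation email (Appendix 2) says of their later use: "Your participation at this point will not be recorded". No section states a per-protocol criterion for waitlist participants, or whether they belong to the set.

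The Adherence section measures module completion by "tracking access online web page hits, documents downloaded or requested in hard copy", and also by diaries. The Acceptability section adds a short questionnaire after each online session.

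**The concern.** The definition can be met in one arm only, yet it is meant to support a comparison between arms. The set therefore has no comparator, or it has one that was not filtered in the same way as the intervention arm.

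In the second case, randomisation no longer protects the comparison. Who opens four modules of a self-paced programme is decided after allocation. The Introduction and Appendix 1 (module 1) link fatigue to low mood, anxiety, apathy and reduced motivation, and these could plausibly also affect who keeps going. Outcomes are unblinded self-reports. The text presents this set as one in which the assessment of efficacy is safe from bias, so a reader may give it more trust than it can bear.

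The pilot's first aim is to use the between-group difference in change to size a full trial. An adherers-only difference that found its way into that calculation could mislead it.

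**Working it through.** **1. The Protocol's own figure.** 20 per arm at 1:1 gives 2 × 20 = 40, as stated under Sample size. The number rests on a rule of thumb. No alpha, power, effect size or SD is given, so there is no power calculation to reproduce.

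**2. Apply the rule to each arm.**

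| Arm | Programme access before week 12 | Can meet the four-module rule by the endpoint |
|---|---|---|
| ReFresh (20) | Yes, from allocation | 0 to 20 |
| Waitlist (20) | None; link at week 14 (Design) or week 16 (Randomisation and stratification; Appendix 2) | 0 |

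The two access dates conflict and must be reconciled, but both fall after the 12-week endpoint, so this point does not depend on which one stands. On the literal reading the set is at most 20 ReFresh participants and 0 controls, and no between-arm t test exists.

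**3. Size of the selection bias if all controls are kept.** Let p be the share of the ReFresh arm reaching four modules. Let δ be the difference in 12-week change, in SD units, between those who reach four modules and those who do not, when the programme has no effect (positive if adherers do better). With zero true effect, the expected control mean equals the whole ReFresh-arm mean, so

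bias = mean(adherers) − [p × mean(adherers) + (1 − p) × mean(non-adherers)] = (1 − p) × δ.

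The Protocol gives neither p nor δ. Both are assumptions here:

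- p = 0.8, δ = 0.25: 0.2 × 0.25 = 0.05 SD
- p = 0.6, δ = 0.50: 0.4 × 0.50 = 0.20 SD
- p = 0.5, δ = 0.75: 0.5 × 0.75 = 0.375 SD
- δ = 0: no bias at any p
- δ negative: same sizes, opposite sign

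**4. Cross-check with a second model.** Let adherence tendency correlate ρ with outcome, so that bias = ρ × φ(z)/p, where φ is the standard normal density and z the (1 − p) quantile. Simulation used 20,000 trials per setting, zero true effect, a two-sided 5% t test, and 20p adherers against 20 controls:

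| p | ρ | Bias (formula) | Type I error |
|---|---|---|---|
| 0.8 | 0.3 | 0.105 SD | 5.9% |
| 0.6 | 0.3 | 0.193 SD | 8.3% |
| 0.5 | 0.5 | 0.399 SD | 16.4% |

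Over p = 0.5 to 0.9 and ρ = 0.2 to 0.5 the bias runs from 0.04 to 0.40 SD. At ρ = 0 it is zero and the type I error stays at about 5%.

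**5. Precision, for scale (95% half-widths, t quantiles).**

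- Intention-to-treat, 20 against 20: 2.024 × √(1/20 + 1/20) = 2.024 × 0.316 = 0.64 SD
- Per-protocol at p = 0.6, 12 against 20: 2.042 × √(1/12 + 1/20) = 2.042 × 0.365 = 0.75 SD
- Complier average causal effect (intention-to-treat estimate divided by p) at p = 0.6: about 0.64/0.6 = 1.07 SD

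**The case against.** The natural reading is that the threshold belongs to the ReFresh arm: it reappears under Intervention group, and waitlist participants have no module requirement to breach. That is fair. A reader might infer that the sponsor intends a set without controls, and the text does not support that. But the rule is written in the Protocol, and as written it does not say that controls stay in.

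On that natural reading, the remaining problem is the familiar limit of any adherence-based analysis, in a pilot that makes intention-to-treat primary and disclaims an accurate assessment of efficacy. This stands, and it limits the weight of the point. It does not excuse describing the set by its freedom from bias.

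A reader might also infer that the per-protocol result must favour ReFresh. The documents do not show this. People whose fatigue is worsening might engage more, which would reverse the sign. Because the outcome is change from baseline, stable differences between adherers and non-adherers largely cancel. The illustrative 0.20 SD also lies well inside the per-protocol half-width of 0.75 SD.

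Two further inferences should be resisted. The count does not rest on page hits alone, since downloads, diaries and per-session questionnaires are collected too; the Protocol simply does not say which of them determines the four-module count. And nothing says that the per-protocol difference will feed the sample size of the definitive trial.

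The strongest objection is to a complier average causal effect as a replacement. Exercise is promoted in every module, so opening one to three modules may have an effect. Knowing one's allocation may shift self-report, and dividing by p enlarges that shift: an assumed 0.20 SD becomes 0.20/0.6 = 0.33 SD. This stands, and is why the estimate is proposed as an addition with its assumptions stated.

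**Conclusion.** The point holds as a defect in how a secondary analysis is defined. The stated rule gives either a set with no controls, on which the planned test cannot be run, or a comparison of self-selected adherers with an unselected control arm. The first follows from the access dates alone and needs no assumption. In the second, selection bias is possible but neither its sign nor its size is known. It is about 0.05 to 0.38 SD towards benefit if 50 to 80% adhere and adherers would have changed 0.25 to 0.75 SD better than non-adherers regardless. It is zero if adherence is unrelated to change, and reversed if adherers would have done worse. The primary intention-to-treat analysis is unaffected. The change is worth making because it is cheap and because the present wording claims a protection that the set does not give.

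**What to change.** In Efficacy Analyses:

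1. State that the four-module threshold applies to the ReFresh arm only and that all waitlist participants are retained.
2. Remove the implication that this set protects the efficacy assessment from bias.
3. Label the per-protocol result descriptive, and state that it will not be used to size the definitive trial.
4. Add, without necessarily replacing the per-protocol result, an exploratory complier average causal effect: two-stage least squares with allocation as instrument, reaching four modules as exposure and baseline score as covariate. State that it assumes no effect of fewer than four modules and no effect of allocation itself on unblinded self-report.
5. Base the four-module count on participant-level records, for example the questionnaire already planned after each session, and not on page hits alone.

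The cost is a few sentences, one extra model, and a participant identifier on the session questionnaires if they do not already carry one. The downside is precision: the complier interval is about 1/p times the intention-to-treat width, roughly ±1.07 SD against ±0.64 SD at 20 per arm and p = 0.6, so it will be informative only as an exploratory figure.
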